11.3 Reporting of Serious Adverse Events and Unanticipated Problems

Investigators and the protocol sponsor will conform to the adverse event reporting timelines, formats and requirements of the various entities to which they are responsible, but at a minimum those events that must be reported are those that are:

- related to study participation,
- unexpected, and
- serious or involve risks to subjects or others (see definitions, section 8.1).

For Narrative Reports of Safety Events

If the report is supplied as a narrative, the minimum necessary information to be provided at the time of the initial report includes:

- Study identifier
- Study Center
- Subject number
- A description of the event
- Date of onset
- Current status
- Whether study treatment was discontinued
- The reason why the event is classified as serious
- Investigator assessment of the association between the event and study treatment

11.3.1 Investigator reporting: notifying the study sponsor

The following describes events that must be reported to the study sponsor in an expedited fashion.

Initial Report: within 24 hours:

The following events must be reported to the study sponsor by telephone within 24 hours of awareness of the event:

- Unanticipated problems related to study participation,
- Serious adverse events, regardless of whether they are unexpected.

Follow-up report: within 48 hours:

As a follow-up to the initial report, within the following 48 hours of awareness of the event, the investigator will provide further information, as applicable, on the unanticipated device event or the unanticipated problem in the form of a written narrative. This should include a copy of the completed Unanticipated Problem form, and any other diagnostic information that will assist the understanding of the event. Significant new information on ongoing unanticipated adverse device effects shall be provided promptly to the study sponsor.

Other Reportable events:

- **Deviations from the study protocol**

Deviations from the protocol must receive the investigator's IRB approval before they are initiated. Any protocol deviations initiated without Sponsor and the investigator's IRB approval that may affect the scientific soundness of the study, or affect the rights, safety, or welfare of study subjects, must be reported to the Sponsor and to the investigator's IRB as soon as a possible, but **no later than 5 working days** of the protocol deviation.

- **Withdrawal of IRB approval**

An investigator shall report to the sponsor a withdrawal of approval by the investigator's reviewing IRB as soon as a possible, but **no later than 5 working days** of the IRB notification of withdrawal of approval.

11.3.2 Investigator reporting: notifying the IRB

Federal regulations require timely reporting by investigators to their local IRB of unanticipated problems posing risks to subjects or others. The following describes the NYULMC IRB reporting requirements, though Investigators at participating sites are responsible for meeting the specific requirements of their IRB of record.

Report Promptly, but no later than 5 working days:

Researchers are required to submit reports of the following problems promptly but no later than 5 working days from the time the investigator becomes aware of the event:

- **Unanticipated problems including adverse events that are unexpected and related**
 - *Unexpected: An event is "unexpected" when its specificity and severity are not accurately reflected in the protocol-related documents, such as the IRB-approved research protocol, any applicable investigator brochure, and the current IRB-approved informed consent document and other relevant sources of information, such as product labeling and package inserts.*
 - *Related to the research procedures: An event is related to the research procedures if in the opinion of the principal investigator or sponsor, the event was more likely than not to be caused by the research procedures.*
 - *Harmful: either caused harm to subjects or others, or placed them at increased risk*

Other Reportable events:

The following events also require prompt reporting to the IRB, though **no later than 5 working days**:

- **Complaint of a research subject** when the complaint indicates unexpected risks or the complaint cannot be resolved by the research team.
- **Protocol deviations or violations** (includes intentional and accidental/unintentional deviations from the IRB approved protocol) for any of the following situations:
 - *one or more participants were placed at increased risk of harm*

- *the event has the potential to occur again*
- *the deviation was necessary to protect a subject from immediate harm*

- **Breach of confidentiality**
- **Incarceration of a participant** when the research was not previously approved under Subpart C and the investigator believes it is in the best interest of the subject to remain on the study.
- **New Information indicating a change to the risks or potential benefits** of the research, in terms of severity or frequency. (e.g. analysis indicates lower-than-expected response rate or a more severe or frequent side effect; Other research finds arm of study has no therapeutic value; FDA labeling change or withdrawal from market)

Reporting Process

The reportable events noted above will be reported to the IRB using the form: “Reportable Event Form” or as a written report of the event (including a description of the event with information regarding its fulfillment of the above criteria, follow-up/resolution and need for revision to consent form and/or other study documentation).

Copies of each report and documentation of IRB notification and receipt will be kept in the Clinical Investigator’s study file.

11.4 Stopping Rules

In this study, if we encounter any serious adverse events or > 5 adverse events in general we will interrupt the study and monitor for etiology and reasons behind the study. These events will be reported to the IRB as noted above.

11.5 Data and Safety Monitoring Plan

It is the responsibility of the Principal Investigator to oversee the data and safety monitoring plan. The PI as well as co-investigator [name] will be conducting the data safety monitoring review. We will review all endothelial sampling procedures for any adverse events after each one is performed. Important reviewable events include excess pain, significant bruising, or vagal responses in addition to those listed above in the adverse events section.

All serious adverse events will immediately be reported to the IRB along with a decision and plan on how to prevent these events in the future as detailed above in the reporting of adverse events section. A routine summary report will be sent to the IRB every three months to ensure adequate safety.

Safety will be monitored throughout the longitudinal phase of the study. For the control subjects, 1 week after endothelial vein sampling, a follow up phone call will be performed. For the longitudinal phase of the study with psoriatic subjects, subjects will get a phone call 1 week after the initial endothelial vein sampling, a follow up visit will occur at week 2 in the longitudinal cohort, not just for endothelial vein sampling but also to ensure safety and tolerability when on the aspirin and/or statin. Finally, a phone call will be performed at study week 3, 1 week after the second endothelial vein

sampling procedure was performed. On the consent form, all participants will have access to several phone numbers with the ability to leave a message to talk to study members including the PI, [name] office, and co-investigator [name]'s telephone number. Subjects will be counseled on the potential complications of aspirin and/or statin therapy as detailed above in the consent form and that for medical questions or problems they deem as emergencies including severe bleeding they should phone their own physician or report to the nearest emergency room .

12. Data Handling and Record Keeping

12.1 Confidentiality

This study is for research purposes only. Individual result will not be given back to study participant. This will include information from final results of the study, interim results of the study and incidental findings. Confidentiality will be preserved to the fullest extent by the research team. All data will be stored with a unique code that does not identify the subject. Initial study data will be recorded on a printed form, which will be later converted to an IRB approved electronic database, REDCap. Only study personnel will have access to this database. Furthermore, data will be saved using a double electronic lock. All physical data will also be kept under double physical lock.

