Subclinical Cardiovascular Disease in Psoriatic Disease

Principal Investigator

[name], MS, FAHA, FACC
Associate Professor of Medicine (Cardiology and Hematology)
The Center for the Prevention of Cardiovascular Disease
New York University School of Medicine
[name]
[name]
[contact]
[contact]
e-mail: [contact]

Study Investigators

[name]
Post-doctoral research Fellow
The Center for the Prevention of Cardiovascular Disease
New York University School of Medicine
[name]
[name]
[contact]
[contact]
e-mail: [contact]

1. Synopsis

Cardiovascular disease (CVD) remains the leading cause of death in the US. Five modifiable risk factors: smoking, hyperlipidemia, diabetes, hypertension and obesity, account for 50% of CVD mortality between the ages of 45 – 79.¹ These traditional cardiac risk factors dictate who to treat with primary prevention measures but do not take into account patient-specific disease states such as psoriatic disease including psoriasis and psoriatic arthritis, which predispose to chronic inflammation. Patients with psoriatic disease have an increased risk of atherosclerotic heart disease and myocardial infarctions compared to matched controls.² Studies are needed on how the chronic inflammation seen in psoriatic disease translates into the increased atherosclerotic and thrombotic risk and how treatment reduces this CVD risk.

2. Background and significance

Psoriatic disease which includes psoriasis and psoriatic arthritis are chronic inflammatory disease states which have been shown to increase the risk of cardiovascular mortality.³ Psoriasis has a prevalence of 2 to 3 percent, with a bimodal distribution affecting most those 30 – 39 and again between 50 – 69 years of age.⁴ Meta-analysis on the association of CVD with psoriasis have yielded an overall relative risk (RR) of 1.5 for ischemic heart disease.⁵ Young adults are at even higher relative risk (RR) higher risk, with a RR for myocardial infarction of 3.1 compared to age-matched controls.⁶ Confounding this relationship is the increased prevalence of metabolic syndrome, obesity, HTN and hyperlipidemia within the psoriatic population.⁵ Despite this, epidemiologic studies have noted the increased risk of CVD remains after adjustment for these traditional CVD risk factors.⁶

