4.4 Informed consent

If a subject wishes to participate, a member of the research team will review the informed consent documents, answer any questions, and obtain written consent for participation in the study and obtain written consent for future analysis, contact, and sample storage. Subjects will be given a "Subject history form" to fill out asking for a complete medical history. They will also be given an appointment reminder sheet to bring with their consent form. They will bring the subject history form to their first baseline assessment appointment. Participants will consent to complete the baseline assessments (see table 1). Participants may opt to decline participation in any baseline assessment they feel uncomfortable with or time constraints do not allow. Follow-up assessments will be completed in those who agree to aspirin or atorvastatin usage for the longitudinal part of the analysis. Participation in follow-up assessment is not required for participation in the baseline assessment. The consent process will take place in private offices at the NYU FGP, CTSI, ambulatory care center, Seligman Center for Advanced Therapeutics and Bellevue adult clinics. Subjects will be given the opportunity to be contacted for future studies that they may qualify for as well. A member of the research team will conduct the baseline interview with the subject and review the clinical history, demographic information and medication use with the individual. All information including the consent will be kept under double lock and key at the PI's office in NYU Skirball 9th floor.

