4.5.3 Vascular function assessment

Vascular function may be assessed either using brachial artery flow mediated dilatation (FMD) or pulse wave velocity (PWV), both non-invasive ultrasound measures of vascular function. FMD and PWV will be measured using a duplex ultrasound imaging system (2D, grayscale B-mode imaging, pulsed Doppler and color flow Doppler) with a 11 MHz linear array probe (Sonosite Inc., Bothell WA). Collection of the ultrasound vascular function data will occur in the Clinical Research Center of the NYU Clinical and Translational Science Institute (CTSI), under the direction of [name], who is on this proposal.

Before each study, participants will provide answers to a brief series of questions to determine eligibility for the FMD/PWV measurements and to determine which arm to use. Participants will rest supine for at least 20 minutes before measurements are made. We will attempt to use the right arm for imaging except in a few uncommon circumstances among patients eligible for this study (recent injury with or without casting on the right arm, right mastectomy with lymph node removal, or any other condition that results in immobility, pain, and/or swelling in the right arm or hand). The participants will be positioned to maximize their comfort and to facilitate image acquisition by the sonographer. A standard 3-lead electrocardiogram will be placed on the torso (right upper torso, left upper torso, and left lower torso) as per protocol. Resting supine blood pressure will be measured in the left arm and recorded.

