Mean blood flow velocity (MBFV, cm/sec) will be determined by calculation of the area under the hand-traced curve of the spectral display. Brachial artery diameter and MBFV will be measured at rest, and after transient arterial occlusion induced by inflation of a forearm blood pressure cuff to suprasystolic pressure for 5 minutes. MBFV will be measured for 15 seconds immediately upon release of the occluding cuff; the first 5 beats after release will be averaged. Occlusion of brachial artery blood flow for 5 minutes with suprasystolic pressures may result in mild hand numbness and discomfort that resolves quickly with decompression of the blood pressure cuff without any known clinical sequelae. Brachial artery diameter will be measured over a 1 cm vessel length at end-diastole 60-75 seconds following release of the occluding cuff; 3 diameter measurements will be averaged. FMD will be calculated as the % change in brachial artery diameter after cuff release compared with the resting diameter. Internal and external landmarks will be used to make repeated measurements at the same vessel site. In our laboratory, mean FMD in normal adult subjects mean age 43 years is 5.89% (95% CI 4.53%, 7.23%). Intraobserver coefficient of variance for FMD measurements of the same vessel is 1-2%. Within-subjects coefficient of variance ranges from 5-10% for same day measurements (reliability coefficient for repeated measures 72%) and 15-30% for day-to-day measurements (reliability coefficient for repeated measures 46%). Carotid-to-femoral arterial pulse wave velocity as well as central arterial

pressure (Sphygmacor), a surrogate measure of vascular stiffness associated with long-term risk of cardiovascular event will also be recorded.

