4.5.5 Biospecimen collection

Study blood will be collected by trained staff in the outpatient clinics, Seligman Center for Advanced Therapeutics or in the CTSI. This will occur immediately after endothelial vein harvesting using the same brachial IV site if the subject has agreed to endothelial vein harvesting. If the subject declined endothelial vein harvesting but agrees to a blood draw, then standard techniques of blood drawing will be used as follows. After cleansing of the venipuncture site with an alcohol wipe and removal of excess alcohol with sterile gauze, a tourniquet will be applied to the patient's bicep region. A 20G butterfly needle or less will be inserted into the antecubital vein, the tourniquet will be removed, and free-flowing blood will be collected with minimal trauma and stasis. The needle will be removed when blood collection is complete and sufficient pressure will be applied using sterile gauze at the puncture site until cessation of bleeding. A sterile band-aid will be applied to cover the venipuncture site. .

For each patient, no more than 60 ml (≈4 tablespoons and 1/8 of a standard blood donation) of blood will be collected at the baseline visit in red (no anticoagulant) top, lavender (EDTA anticoagulant) top, green (heparin) and blue (sodium citrate anticoagulant) top tubes). We believe this amount of blood is negligible and presents minimal risk for the patient. Approximately 30 cc of blood will be used for the different measurements of platelet function, lipid levels, coagulation, inflammation, and approximately 30 cc of blood will be used for isolation of RNA, microRNA and storage of DNA at -80C. . The samples will be stored in the PI's lab at the NYU Science building 7th floor without any identifying information other than a code number. These samples will be barcoded system and lab vantage and stored in a freezer with back-up power supply.

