4.5.6 Longitudinal Follow Up Data Collection

Participants enrolled in the longitudinal part of this study will be offered the option to participate in follow-up biospecimen collection. This follow-up will allow us to assess how aspirin and/or atorvastatin affect platelet and endothelial function and inflammation. This follow-up component will consist of additional blood samples of ≈ 30ml (2 tablespoons or less) that will be collected for different measurements of platelet function, lipid levels, coagulation, inflammation, and approximately 30 ccs of blood will be used for isolation of RNA, microRNA and storage of DNA at -80C. The samples will be stored in the PI's lab at the NYU Science building 7th floor without any identifying information other than a code number. Repeat endothelial vein harvesting will also be performed as described above.

Overall, code numbers used for collection of samples will not be based on any information that could be used to identify the subject (for example, social security number, initials or birth date). The master list linking names to code numbers will be kept in a locked file cabinet, separate from all research information.

If participating in the optional follow-up collection, the total amount of blood withdrawn (baseline plus follow up) will be no more than 120 ml (approximately 7 tablespoons and 1/4 for a standard blood donation). This amount of blood collection is within established safety guidelines of research blood collection in adults. Blood collection at baseline and at the follow up time points will allow us to examine how the treatment of aspirin and atorvastatin modify 1) endothelial vein function in psoriatic disease, 2) changes to platelet activity and 3) alterations in coagulation and inflammation in those with psoriatic disease.

For all cases and controls, we will call 1 week after each procedure to assess how patients are feeling after endothelial vein harvesting. Adverse events will be managed as mentioned below.

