11.1 Definitions

Unanticipated Problems Involving Risk to Subjects or Others

Any incident, experience, or outcome that meets all of the following criteria:

- Unexpected in nature, severity, or frequency (i.e. not described in study-related documents such as the IRB-approved protocol or consent form, the investigators brochure, etc)
- Related or possibly related to participation in the research (i.e. possibly related means there is a reasonable possibility that the incident experience, or outcome may have been caused by the procedures involved in the research)
- Suggests that the research places subjects or others at greater risk of harm (including physical, psychological, economic, or social harm).

Adverse Event

An **adverse event** (AE) is any symptom, sign, illness or experience that develops or worsens in severity during the course of the study. Intercurrent illnesses or injuries will be regarded as adverse events. Abnormal results of diagnostic procedures are considered to be adverse events if the abnormality:

- results in study withdrawal
- is associated with a serious adverse event
- is associated with clinical signs or symptoms
- leads to additional treatment or to further diagnostic tests
- is considered by the investigator to be of clinical significance

Serious Adverse Event

Adverse events are classified as serious or non-serious. A ***serious adverse event*** is any AE that is:

- fatal
- life-threatening
- requires or prolongs hospital stay
- results in persistent or significant disability or incapacity
- a congenital anomaly or birth defect
- an important medical event

Important medical events are those that may not be immediately life threatening, but are clearly of major clinical significance. They may jeopardize the subject, and may require intervention to prevent one of the other serious outcomes noted above. For example, drug overdose or abuse, a seizure that did not result in in-patient hospitalization, or intensive treatment of bronchospasm in an emergency department would typically be considered serious.

All adverse events that do not meet any of the criteria for serious will be regarded as ***non-serious adverse events***.

Adverse Event Reporting Period

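### The non-return rule in section 12.1 expressly covers incidental findings and has no exception, so a clinically significant baseline blood pressure would go untold if the plan is followed as written

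*Combined protocol and SAP*

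**What the plan says.** Section 12.1 (Confidentiality) describes the study as research only and states that participants do not receive their individual results. The next sentence sets the scope: "This will include information from final results of the study, interim results of the study and incidental findings". No qualifier follows.

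Three other places point the same way:

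- Section 4.5.7 keeps genetic information from everyone, participants and their physicians included.
- Section 4.6 keeps results of future research from subjects and the study doctor.
- Section 5, under genetic risks, says individual study results are withheld from participants and their physicians. The reason given is that findings will be preliminary and their clinical meaning may take years to emerge.

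The study also collects values that clinicians ordinarily act on. Section 4.5.3: "Resting supine blood pressure will be measured in the left arm and recorded". Section 4.5.5: "Approximately 30 cc of blood will be used for the different measurements of platelet function, lipid levels, coagulation, inflammation". At follow-up (section 4.5.6), blood is again "collected for different measurements of platelet function, lipid levels, coagulation, inflammation". Section 2 notes "the increased prevalence of metabolic syndrome, obesity, HTN and hyperlipidemia within the psoriatic population".

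Section 11.1 deals with abnormal findings as a matter of classification. An abnormal diagnostic result is an adverse event (AE) if, among other criteria, it "is considered by the investigator to be of clinical significance". A clinically significant abnormality found at screening is logged as a preexisting condition, and such a condition becomes an AE only if it worsens.

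**The concern.** Not returning results is sensible for genetic and exploratory data, and section 5 gives a reason for it. Section 12.1 goes further. It names incidental findings as withheld, so the rule reaches a blood pressure reading as readily as a transcript count. High blood pressure is usually silent. The safety contacts in sections 11.2 and 11.5 (questioning, phone calls, the week-2 visit) pick up what a participant can feel and report, and so are unlikely to bring out a reading that only the staff have seen.

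At stake is whether a participant with a clinically significant reading leaves the visit without being told. The plan itself expects more hypertension and hyperlipidemia in the psoriatic group. Current statin users are excluded (sections 4.2 and 4.3), so a high baseline lipid value would belong to someone not on a statin.

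**Working it through.** No figure in the plan bears on this point, so there is none to reproduce. The check is a reading of the whole supplied text for any route by which a participant would learn of a finding, followed by a simple count.

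**Possible routes to disclosure**

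| Place | What it provides | Does it tell the participant? |
|---|---|---|
| 4.5.3, vascular assessment | Resting blood pressure taken and recorded | No action threshold or notification step |
| 4.5.2, end of study | Referral to the primary provider | Only for continuing the study drugs |
| 11.1, screening abnormalities | Logged as a preexisting condition | No instruction |
| 11.1, abnormal laboratory values | Documented as an AE, for example if active management is needed | Implied at most; it is a criterion for documentation |
| 11.2, recording AEs | Events followed to resolution or stabilization | Implied at most, and only once something is an AE |
| 11.3.1, 11.3.2, 11.5, reporting | Reports to the sponsor and the IRB | No |
| 12.1 and section 5 | Results withheld; section 5 adds physicians | Barred |

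No row is written as an exception to section 12.1.

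**A high resting blood pressure at baseline, followed through the plan**

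1. It is measured and recorded (4.5.3).
2. As a baseline abnormality it is at most logged as a preexisting condition (11.1).
3. It becomes an AE only on worsening. The planned follow-up lists blood, vein harvesting and medical history (4.5.2 and Table 1), with no repeat of the imaging visit at which blood pressure is taken.
4. Section 12.1 bars telling the participant. Section 5, read literally, bars telling the physician.

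**Lipid and coagulation values.** The same path applies only if the assay is run to a clinical standard and the result is seen while the participant is on study. The documents state neither.

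**Planned numbers**

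- Participants (Table 1 and section 9, as recruitment goals): 40 + 10 = 50, of whom 40/50 = 80% are psoriatic. Fewer will have a baseline imaging reading if some decline imaging, as sections 4.4 and 4.5.1 allow.
- Follow-up blood draws: 40 if all four offered groups return (4.5.2). Section 4.4 reads more narrowly: "Follow-up assessments will be completed in those who agree to aspirin or atorvastatin usage for the longitudinal part of the analysis". On that reading, 3/4 × 40 = 30.
- Blood draws in total: 50 + 30 = 80 to 50 + 40 = 90. The number that matters here could be 0, for the reasons above.

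The documents give no rate of clinically significant readings, so no expected count is computed.

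**The case against.** The strongest reply has four parts.

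*The consent form is unseen.* It was removed from the supplied text, and sections 11.5 and 12.2 show that it covers risks, contacts and handling of information. It may contain an incidental-findings provision. This stands as a limit: a reader might infer that participants are in fact never told, and the documents do not support that. A consent provision would, however, leave the protocol rule in place and the two in conflict.

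*Non-return is deliberate.* Four sections decline to return results, and section 5 explains why. That reason fits genetic and exploratory data and should be respected there. It does not fit a blood pressure reading, whose meaning is known on the day.

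*Section 11 governs clinically significant abnormalities.* Changing a dose, stopping a drug or ordering tests would ordinarily involve the participant. This has force for abnormalities that arise on treatment. A reader might therefore infer that 12.1 contradicts section 11. It does not: section 11 never says the participant is told, so the two are only in tension. For a baseline abnormality the reply is weak, because section 11.1 does no more than log it.

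*The size is easily overstated.* A reader might infer that the imaging visit supplies the only blood pressure in the study. That is not supported: section 4.5.3 also records central arterial pressure, and sections 11.1 and 11.2 refer to physical examination. A reader might also treat 50 as a ceiling, but the 40 and 10 are goals. Nor can one conclude that abnormal lipid or coagulation results would be withheld in time to matter.

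**Conclusion.** The point holds for blood pressure. Sections 12.1 and 5, as written, would have the investigator record a clinically significant baseline reading and tell neither the participant nor the physician. An investigator who told the participant anyway would be departing from 12.1. For lipid and coagulation values the point is conditional on assay validity and timing.

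It rests on three assumptions: that 12.1 is applied literally, that section 5's sentence is not already understood as limited to genetic results (its position suggests it might be), and that the consent form does not override the rule. About 50 participants are planned; the number who would have an actionable finding is unknown and may be small. Sample size, error rates and analyses are not touched. This is a cheap improvement for patient safety, of low severity.

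**What to change.** 1. In section 12.1, limit non-return to genetic, transcriptomic and exploratory research-assay results. Include flow-mediated dilatation, pulse wave velocity and the Sphygmacor central pressure in that group. The protocol sets no clinical action threshold for them, and section 4.5.3 gives a day-to-day reliability coefficient of only 46% for flow-mediated dilatation.
2. In section 5, limit the sentence about participants and their physicians expressly to genetic results. Without this, telling a treating physician would still conflict with the text.
3. Add to section 12.1: *A vital-sign or clinically valid laboratory finding that the investigator judges clinically significant will be told to the participant and, with permission, to the treating physician, and handled under section 11 where it meets the AE definition.*
4. Check that the consent form agrees.

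The cost is two limiting phrases, one sentence and a consent check, then a few notifications, some of them false alarms. Keeping the vascular research measures out holds that number down. The genetic policy, endpoints, analyses and sample size stay as they are.
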